6.5.3 Study drug compliance and accountability

6.5.3.1 Study drug compliance

Compliance will be assessed by the investigator and/or study personnel at each patient visit and information provided by the patient and/or caregiver will be captured in the Drug Accountability Form. This information must be captured in the source document at each patient visit.

6.5.3.2 Study drug accountability

The investigator or designee must maintain an accurate record of the shipment and dispensing of study treatment in a drug accountability log. Drug accountability will be noted by the field monitor during site visits and at the completion of the study. Patients will be asked to return all unused study treatment and packaging on a regular basis, at the end of the study or at the time of study treatment discontinuation.

At study close-out, and, as appropriate during the course of the study, the investigator will return all unused study treatment, packaging, drug labels, and a copy of the completed drug accountability log to the IQVIA monitor or to the IQVIA address provided in the investigator folder at each site.

6.5.3.3 Handling of other study treatment

Not applicable.

6.5.4 Disposal and destruction

The drug supply can only be destroyed once the study drug accountability check has been performed by the monitor. The study drug supply can be destroyed at the local Recordati facility, by Drug Supply group or by a third party, as appropriate.

7 Visit schedule and assessments

7.1 Study flow and visit schedule

[Table 7-1](#) lists all of the assessments and indicates with an “X”, the visits when they are performed. All data obtained from these assessments must be supported in the patient’s source documentation.

The table indicates which assessments produce data to be entered into the database (D) or remain in source documents only (S) (“Category” column).

Table 7-1 Visit evaluation schedule

7.1.1 Molecular pre-screening

Not applicable.

7.1.2 Screening

There will be no screening period for this study. At the enrollment visit, the patient will need to complete a written informed consent. Once consented, patients will be evaluated for eligibility via the inclusion and exclusion criteria.

7.1.2.1 Eligibility screening

Not applicable.

7.1.2.2 Information to be collected on screening failures

Not applicable.

7.1.2.3 Patient demographics and other baseline characteristics

For patients who are eligible to participate in this roll over study, an e-CRF will be completed that identifies the patients' gender, date of birth and previous study, site /center and subject number. Study dose, formulation and frequency, study indication and relevant medical history will also be collected.

7.1.3 Treatment period

The starting dose of pasireotide, and any medication given in combination with pasireotide, should be the same dose as that which the patient was receiving in the parent study at roll over.

Those patients receiving pasireotide LAR must return to the study center monthly (+/- 7 days) to receive study medication. Drug dispensing information will be collected and adverse events and clinical benefit will be assessed. Patients receiving pasireotide s.c. must return to the study center on a quarterly basis (every 12 weeks +/- 2 weeks) for resupply of study medication. Drug dispensing information will be collected and adverse events and clinical benefit will be assessed. The patient may return to the clinic at any given time as per standard of care or treating physician recommendation; however, only the quarterly study visits will be recorded. The study is expected to remain open for approximately 10 years from FPFV (or until 10-Jun-2023 in the UK) or when all patients on this study have permanently discontinued pasireotide treatment or have been able to obtain commercial supply according to local regulations or have been able to receive the drug through country-specific programmes outside of this clinical trial (applicable to Brazil, France, Germany, India, Italy, Malaysia, Mexico, Peru and Thailand) and the end of treatment visit and all safety follow-up procedures have been performed for each patient, whichever comes first. At every visit, the investigator is required to confirm that the patient continues to have clinical benefit and may continue receiving study treatment.

7.1.4 Pregnancy and assessment of fertility

Since highly effective contraception is required during the study, female patients of child bearing potential are required to test negative for a pregnancy (either with serum testing if routinely/locally available or urine pregnancy test) before enrolling into the study.

Women of child-bearing potential, defined as all women physiologically capable of becoming pregnant, **unless** they are using highly effective methods of contraception during the study and for 30 days after the final dose of pasireotide s.c. and 84 days after the final dose of pasireotide LAR.

Highly effective contraception is defined as either:

- Total abstinence (when this is in line with the preferred and usual lifestyle of the patient. Periodic abstinence (e.g., calendar, ovulation, symptothermal, post-ovulation methods) and withdrawal are not acceptable methods of contraception.
- Female sterilization (have had surgical bilateral oophorectomy with or without hysterectomy) or tubal ligation at least six weeks before taking study treatment. In case of oophorectomy alone, only when the reproductive status of the woman has been confirmed by follow up hormone level assessment.
- Male sterilization (at least 6 months prior to enrolling). For female patients on the study the vasectomized male partner should be the sole partner for that patient.
- Use of oral, injected or implanted hormonal methods of contraception or placement of an intrauterine device (IUD) or intrauterine system (IUS), or other forms of hormonal contraception that have comparable efficacy (failure rate <1%), for example hormone vaginal ring or transdermal hormone contraception.

If patient has tested negative at the end of study on the parent study, no pregnancy testing is required if enrollment into this study is carried out on the same day or within a maximum of 5 days from each other.

Female patients of child bearing potential are required to perform monthly home urine pregnancy tests and complete a simple diary with the dates and the outcome of the home urinary test while on study treatment and during safety follow-up (30 days after the final dose of pasireotide s.c. and 84 days after the final dose of pasireotide LAR).

A pregnancy test (either with serum testing if routinely/locally available or urine pregnancy test) on female patients of child bearing potential is required at the final study visit.

Any positive results will be recorded in the database and followed up as per [Section 8.4](#).

7.1.5 Discontinuation of study treatment

Patient may voluntarily discontinue from the study treatment for any reason at any time. If a patient decides to discontinue from the study treatment, the investigator should make a reasonable effort (e.g. telephone, e-mail, letter) to understand the primary reason for this decision and record this information in the patient's chart and on the appropriate CRF pages. They may be considered withdrawn if they state an intention to withdraw, fail to return for visits, or become lost to follow-up for any other reasons.

At the time the patient discontinues study treatment, a visit should be scheduled as soon as possible, at which time the assessments listed for the End of Treatment (EOT) visit will be performed. End of Treatment information will be completed in the eCRF giving the date and reason for stopping the study treatment (see [Section 7.1.5.1](#)).

At a minimum, all patients who discontinue study treatment, including those who refuse to return for a final visit, will be contacted for safety evaluations 1 month following last dose of the s.c. dose or 3 months for patients receiving LAR, following last dose. The completion of the Study Evaluation Completion CRF page will be required any time a patient discontinues from the study and must be completed 30 days after the end of treatment.

7.1.5.1 Criteria for premature patient withdrawal

Patients may voluntarily withdraw from the study or be dropped from it at the discretion of the investigator at any time. Patients may be withdrawn from the study if any of the following occur:

- Death.
- Lost to follow-up.
- Staying in the study would be harmful.
- Patient/guardian decision.
- Physician decision.
- Non-compliance to protocol requirements.
- Protocol deviation.
- Pregnancy.
- Study terminated by sponsor.
- Study treatment has become available through country-specific programmes outside of this clinical trial (applicable to Brazil, France, Germany, India, Italy, Malaysia, Mexico, Peru and Thailand).

Study treatment has become commercially available and reimbursed (when current treatment becomes commercially available and reimbursed in that indication, the patient will have to be withdrawn from the study and will have completed the study as per protocol).

In addition to the general withdrawal criteria, the following criteria may also require study treatment discontinuation:

If any of the criteria below are met during routine examinations that are part of standard of care, study medication should be discontinued immediately. Re-challenge of study medication is prohibited once discontinuation criteria are met.

Hepatic-related discontinuation criteria

- Jaundice or other signs of clinically significant liver dysfunction
- ALT or AST $> 3 \times$ ULN and Total Bilirubin $\geq 2 \times$ ULN and ALP $< 2 \times$ ULN
- ALT or AST $> 5 \times$ ULN and $\leq 8 \times$ ULN persistent for more than 2 weeks
- ALT or AST $> 8 \times$ ULN

QT related discontinuation criteria

- Confirmed QTcF >500 ms and discontinuation recommended by a cardiologist
- QTcF > 480 msec, if the investigator determines it is no longer safe for the patient to continue in the study, based on ECGs, cardiac examination and recommendation from a cardiologist.
- Clinically significant arrhythmias including:
 1. Any ventricular or supra-ventricular tachyarrhythmia associated with symptoms of hemodynamic compromise.
 2. Sustained ventricular tachycardia (>30 s) irrespective of symptoms.
 3. Recurrent non-sustained VT (≥ 3 beats) during any 24-hour monitoring period.
 4. Clinically significant brady-arrhythmia or third degree AV block.
 5. Need to use a drug with known risk of TdP.

Hyperglycemia related discontinuation criteria

- Uncontrolled diabetes mellitus (DM), consistently high glucose values FPG ≥ 240 mg/dL (13.3 mmol/L) or HbA1c value ≥ 10 % despite appropriate management of diabetes including diet and/or exercise with or without optimal anti-diabetic therapy

7.1.5.2 Replacement policy

Not applicable.

7.1.6 Withdrawal of consent

Patients may voluntarily withdraw consent to participate in the study for any reason at any time. Withdrawal of consent occurs only when a patient does not want to participate in the study any longer, and does not want any further visits or assessments, and does not want any further study related contact.

Recordati will continue to retain and use all research results that have already been collected for the study evaluation. All biological samples that have already been collected may be retained and analyzed at a later date (or as required by local regulations).

If a patient withdraws consent, the investigator should make a reasonable effort (e.g. telephone, e-mail, letter) to understand the primary reason for this decision and record this information.

Study treatment must be discontinued and no further assessments conducted.

Further attempts to contact the patient are not allowed unless safety findings require communication or follow up.

7.1.7 Follow up for safety evaluations

All patients must have safety evaluations 84 days after the last dose of study treatment for the LAR and 1 month (30 days) after s.c. dose.

Patients lost to follow up should be recorded as such on the eCRF. For patients who are lost to follow-up, the investigator should show "due diligence" by documenting in the source documents steps taken to contact the patient, e.g., dates of telephone calls, registered letters, etc.

Data collected should be added to the Adverse Events eCRF.

7.1.8 Lost to follow-up

For patients whose status is unclear because they fail to appear for study visits without stating an intention to withdraw consent, the investigator should show "due diligence" by contacting the patient, family or family physician as agreed in the informed consent and by documenting in the source documents steps taken to contact the patient, e.g. dates of telephone calls, registered letters, etc. A patient should not be considered lost to follow-up until due diligence has been completed. Patients lost to follow up should be recorded as such on the appropriate Disposition CRF.

7.2 Assessment types

7.2.1 Efficacy assessments

Not applicable.

7.2.2 Safety and tolerability assessments

Safety will be monitored by collecting adverse events/serious adverse events at every visit. For details on AE/SAE collection and reporting, refer to [Section 8](#).

In addition, the following applies for safety monitoring:

- For locally approved indications, the safety monitoring guidance in the locally approved prescribing information applies
- For indications that are not yet approved locally, the safety monitoring requirements described in [Section 7.2](#) of the current Investigator Brochure must be followed

Patients may have safety assessments performed by the clinics local laboratory as per investigators judgement and standard of care at any time during the study period.

7.2.2.1 Hepatic related findings

For any hepatic related findings during routine follow up, refer to [Appendix 2](#).

7.2.2.2 QT-related finding

For any QT-related finding during routine follow up, refer to [Appendix 3](#).

7.2.2.3 Hyperglycemia related findings

For any hyperglycemia related finding during routine follow up, refer to [Appendix 4](#).

7.2.2.4 Additional bio-marker assessments

Not applicable.

7.2.3 Resource utilization

Not applicable.

7.2.4 Patient reported outcomes

Not applicable.

8 Safety monitoring and reporting

8.1 Adverse events

8.1.1 Definitions and reporting

An adverse event is defined as the appearance of (or worsening of any pre-existing) undesirable sign(s), symptom(s), or medical condition(s) that occur after patient's signed informed consent has been obtained.

Abnormal laboratory values or test results occurring after informed consent constitute adverse events only if they induce clinical signs or symptoms, are considered clinically significant, require therapy (e.g., hematologic abnormality that requires transfusion or hematological stem cell support), or require changes in study medication(s).

Any ongoing adverse events from the parent study will be captured as medical history in the roll-over database. Any AE that begins (or worsens) after signing of the informed consent for the roll-over and during the 30-day (or 28-day) or 84-day (12 week) safety follow up period defined in the parent protocol should be reported in both clinical databases.

Adverse event monitoring should be continued for at least 30 days for patients receiving the s.c. formulation and 84 days for those receiving the LAR formulation (or 5 half-lives), whichever is longer) following the last dose of study treatment. Adverse events (including lab abnormalities that constitute AEs) should be described using a diagnosis whenever possible, rather than individual underlying signs and symptoms. When a clear diagnosis cannot be identified, each sign or symptom should be reported as a separate Adverse Event.

Adverse events will be assessed according to the current version of Common Terminology Criteria for Adverse Events (CTCAE).

If CTCAE grading does not exist for an adverse event, the severity of mild, moderate, severe, and life-threatening, corresponding to Grades 1 - 4, will be used. CTCAE Grade 5 (death) will not be used in this study; rather, information about deaths will be collected through the EOT eCRF page.

The occurrence of adverse events should be sought by non-directive questioning of the patient (subject) during the screening process after signing informed consent and at each visit during the study. Adverse events also may be detected when they are volunteered by the patient (subject) during the screening process or between visits, or through physical examination, laboratory test, or other assessments. As far as possible, each adverse event should be evaluated to determine:

1. The severity grade (CTCAE Grade 1-4)
2. Its duration (start and end dates)
3. Its relationship to the study treatment (reasonable possibility that AE is related: No, Yes)

4. Action taken with respect to study or investigational treatment (none, dose adjusted, temporarily interrupted, permanently discontinued, unknown, not applicable)
5. Whether medication or therapy was given (no concomitant medication/non-drug therapy, concomitant medication/non-drug therapy)
6. Whether it is serious, where a serious adverse event (SAE) is defined as in [Section 8.2.1](#).

If the event worsens the event should be reported a second time in the CRF noting the start date when the event worsens in toxicity. For grade 3 and 4 adverse events only, if improvement to a lower grade is determined a new entry for this event should be reported in the CRF noting the start date when the event improved from having been Grade 3 or Grade 4.

All adverse events should be treated appropriately. If a concomitant medication or non-drug therapy is given, this action should be recorded on the Adverse Event CRF.

Once an adverse event is detected, it should be followed until its resolution or until it is judged to be permanent, and assessment should be made at each visit (or more frequently, if necessary) of any changes in severity, the suspected relationship to the study treatment, the interventions required to treat it, and the outcome.

Progression of malignancy (including fatal outcomes), if documented by use of appropriate method (for example, as per RECIST criteria for solid tumors or as per Cheson's guidelines for hematological malignancies), should not be reported as a serious adverse event.

Adverse events separate from the progression of malignancy (example, deep vein thrombosis at the time of progression or hemoptysis concurrent with finding of disease progression) will be reported as per usual guidelines used for such events with proper attribution regarding relatedness to the drug.

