1.1.4 Overview of other pituitary tumors and of Ectopic ACTH secreting (EAS) tumors

Pituitary adenomas are benign neoplasms arising from one of the five anterior pituitary cell types. The clinical and hormonal syndrome associated with pituitary adenomas depend on the cell type from which they are derived. Tumors arising from lactotrope (PRL), somatotrope (GH), corticotrope (ACTH), thyrotrope (TSH), or gonadotrope (LH, FSH) cells hypersecrete their respective hormones. About one-third of all pituitary adenomas are clinically non-functioning (nonfunctional pituitary adenomas, NFPA) and produce no distinct clinical hypersecretory syndrome. Nelson's syndrome is associated with local corticotroph (ACTH) pituitary tumor re-growth, extension or invasion, following a therapeutic bilateral adrenalectomy to control hypercortisolism, as a result of the removal of the negative feedback of cortisol on hypothalamic corticotropin-releasing hormone. Symptoms result from local tumor expansion, and from effects on other pituitary hormones and on ACTH related symptoms.

Hypersecretion of ACTH can also occur from non-pituitary tumors and is designated as Ectopic ACTH secreting (EAS) tumors. The majority of these patients have non-resectable, advanced or metastatic tumors. Symptoms are related to hypersecretion and tumor burden or mass. Prognosis is usually very poor.

Medical therapy is the main measure to alleviate the symptoms of the above diseases by controlling hyper-secretion of respective hormones. Somatostatin analogues are currently used as a medical therapy option in some of these patients. A phase 2 proof of concept study SOM230D2203 is ongoing evaluating the effect of pasireotide LAR in these tumors.

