8.2 Serious adverse events

8.2.1 Definitions

Serious adverse event (SAE) is defined as one of the following:

- Is fatal or life-threatening
- Results in persistent or significant disability/incapacity
- Constitutes a congenital anomaly/birth defect
- Is medically significant, i.e., defined as an event that jeopardizes the patient or may require medical or surgical intervention to prevent one of the outcomes listed above
- Requires inpatient hospitalization or prolongation of existing hospitalization,
- Note that hospitalizations for the following reasons should not be reported as serious adverse events:
 - Routine treatment or monitoring of the studied indication, not associated with any deterioration in condition
 - Elective or pre-planned treatment for a pre-existing condition that is unrelated to the indication under study and has not worsened since signing the informed consent
 - Social reasons and respite care in the absence of any deterioration in the patient's general condition
- Note that treatment on an emergency outpatient basis that does not result in hospital admission and involves an event not fulfilling any of the definitions of a SAE given above is not a serious adverse event

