8.2.2 Reporting

To ensure patient safety, every SAE, regardless of suspected causality, occurring after the patient has provided informed consent and until at least 30 days for patients on the s.c formulation and 84 days for patients on the LAR formulation after the patient has stopped study treatment must be reported to IQVIA Safety office within 24 hours of learning of its occurrence. IQVIA, in its turn, will promptly inform Recordati.

Any SAE that begins or worsens after signing of the informed consent for the roll-over and during the safety follow up period defined in the parent protocol should be reported as an adverse event in both clinical databases; however, only one SAE report will be sent to IQVIA.

- Any SAE that begins or worsens **during** the safety follow-up period specified in the parent study should have an SAE report submitted to IQVIA—with the parent protocol study number.
- Any SAE that begins or worsens **after** the safety follow-up period specified in the parent study should have an SAE report submitted to IQVIA with the roll-over protocol study number.

Any additional information for the SAE including complications, progression of the initial SAE, and recurrent episodes must be reported as follow-up to the original episode within 24 hours of the investigator receiving the follow-up information. An SAE occurring at a different time interval or otherwise considered completely unrelated to a previously reported one should be reported separately as a new event.

The date of the informed consent signed for this roll-over study (the roll-over date) is important to determine how SAEs should be reported:

- Any SAEs occurred prior to that date should be reported for the parent protocol, including all the follow up information relevant to such SAEs.
- New SAEs with an onset date after the roll-over date will be reported for this protocol.

It is important to use the right SAE form with the correct protocol number for these two scenarios, to avoid confusion in SAE processing. For a patient already on the roll-over protocol but follow up information is reported for the previous SAEs in the parent protocol, it must be clearly labeled that this is for the parent protocol number.

Any SAEs experienced after the 30 day/84 day safety evaluation follow-up period (or 5 half-lives, if half-life is established, whichever is longer) should only be reported to IQVIA if the investigator suspects a causal relationship to the study treatment.

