- A single occurrence will be counted if there is ≤ 1 day gap between the end date of the preceding AE and the start date of the consecutive AE
- More than one occurrence will be counted if there is > 1 day gap between the end date of the preceding AE and the start date of the consecutive AE

For occurrence, the presence of at least one SAE / SAE suspected to be related to study treatment / non SAE has to be checked in a block e.g., among AE's in a \leq 1 day gap block, if at least one SAE is occurring, then one occurrence is calculated for that SAE.

The number of deaths resulting from SAEs suspected to be related to study treatment and SAEs irrespective of study treatment relationship will be provided by SOC and PT.

Adverse events of special interest / grouping of AEs

The specific categories of AEs of special interest list for SOM230 are listed in attachment 8.2.

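### Protocol 8.1.1 keeps progression of any malignancy, fatal or not, out of SAE reporting; it should do so only for the malignancy that is the patient's studied indication

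*Protocol*

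**What the plan says.** Protocol 8.1.1, on adverse event definitions and reporting, exempts one class of event: "Progression of malignancy (including fatal outcomes), if documented by use of appropriate method" "should not be reported as a serious adverse event". It gives RECIST (solid tumours) and Cheson (haematological malignancies) as examples of suitable documentation. The next paragraph keeps events that are separate from the progression reportable. That limits the rule by type of event, not by indication.

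Protocol 8.2.1 defines an SAE. The first criterion is "Is fatal or life-threatening". The only exclusions listed there concern certain hospitalisations and emergency outpatient care, and one of them is tied to the indication: "Routine treatment or monitoring of the studied indication, not associated with any deterioration in condition". Malignancy is not mentioned.

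Protocol 8.2.2 requires 24-hour reporting of "every SAE, regardless of suspected causality, occurring after the patient has provided informed consent", up to the end of the safety follow-up. It also asks for progression of an SAE already reported to be sent as follow-up within 24 hours.

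The primary endpoint is the frequency and severity of AEs and SAEs (Protocol Table 3-1, SAP Table 5-1), in a study classed as a voluntary PASS (Protocol 10.6). SAP 7.4.1 repeats the AE tables for SAEs and adds a count by SOC and PT that begins "The number of deaths resulting from SAEs suspected to be related to study treatment" and also covers SAEs whatever their relationship to treatment.

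**The concern.** A progression exemption is reasonable where the cancer is the disease being treated: its progression reflects the course of that disease and would otherwise fill the SAE tables. This roll-over study, however, mixes cancer indications with acromegaly, Cushing's disease, pituitary adenoma and dumping syndrome. Protocol 1.1.4 itself says that "Pituitary adenomas are benign neoplasms arising from one of the five anterior pituitary cell types". For such a patient, an unrelated cancer that progresses or proves fatal during treatment is a safety outcome and not the course of the studied disease.

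As written, the same exemption applies to both kinds of patient. It also applies when the investigator suspects the drug, because it depends only on documented progression. The 24-hour report, the SAE form with its relationship assessment for each study treatment, and SUSAR handling all start from an SAE report (Protocol 8.2.2). An event withheld at that step reaches none of them.

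**Working it through.** No stated figure bears on this point, so the check consists of a count of indications and a comparison of the sections.

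**Which parent studies have a malignant indication (SAP Tables 2-1 and 2-2)**

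- Distinct studies: 15 in Table 2-1 (X2404 appears twice) + 2 in Table 2-2 = 17.
- Malignant indication only: X2404 (melanoma), XDE04 (prostate cancer), DIC03 (NET) = 3.
- Mixed: D2203 (NET, other pituitary and EAS), C2110E1 (carcinoid or acromegaly) = 2.
- Non-malignant only: B2201E, C2305, C1202, C2402, C2413 (acromegaly, C1202 being acromegaly or pituitary); B2208E, B2305, G2304, B2411 (Cushing's disease); B2219 (both); X2203 (dumping syndrome); D2401 (pituitary adenomas) = 5 + 4 + 1 + 1 + 1 = 12.
- Check: 3 + 2 + 12 = 17. Adding the NET study D2101 from Protocol Appendix 10, which is not in the SAP tables, gives 12 of 18.

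This counts studies, not patients. Amendment 2 gives 301 patients enrolled by September 2017, with no split by indication.

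**What the sections tell a site to do**

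1. *NET patient whose NET progresses.* 8.1.1 says not to report an SAE. This is the ordinary use of such a rule.
2. *Acromegaly patient with a first diagnosis of cancer on study.* This is not progression, so 8.1.1 does not exempt it. It is an AE, and an SAE if it meets 8.2.1.
3. *The same patient, whose cancer was reported as an SAE and then progresses or is fatal.* 8.1.1 says not to report it as an SAE. 8.2.2 says to send it as follow-up within 24 hours. The instructions are opposite.
4. *Acromegaly patient with a cancer that pre-dates consent, or whose diagnosis was not reported as an SAE, and that progresses with a life-threatening or fatal course.* 8.1.1 says not to report it. 8.2.1 makes it an SAE, and 8.2.2 requires every SAE. No SAE is open to which follow-up could be attached. This is the clearest gap.

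**What remains and what is lost in case 4 if 8.1.1 is followed**

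- Remains: worsening of a pre-existing condition is an AE, with grade and relationship recorded (8.1.1). It enters the treatment-emergent AE tables if it falls in the on-treatment period (SAP 7.4.1). Deaths are collected on the EOT page (8.1.1) and summarised by SOC, PT, indication and formulation (SAP 7.4.2).
- Lost: SAE classification, 24-hour and SUSAR reporting, and entry in the SAE tables and in the counts of deaths attributed to SAEs (SAP 7.4.1). Of the registry tables in SAP 7.4.1, the one for non-serious events has a 5% threshold, so an uncommon progression recorded as non-serious could appear in neither the serious nor the non-serious table.

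**The case against.** The strongest reply is that the sentence is plainly meant as a disease-under-study rule. The next paragraph gives haemoptysis at the time of disease progression as an example, which suggests an oncology setting, and RECIST and Cheson are only examples of documentation. That is a fair account of the likely intent. The text does not state it, though, and 8.2.1 shows that the protocol names the studied indication when it wants that limit. Equally, a reader might take the mention of haematological malignancies as proof that unrelated cancers were meant to be exempt, since no parent indication is haematological. An illustrative list does not carry that weight.

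The second reply is that little is lost, and much of it stands. Progression is still an AE with a relatedness judgement, incident cancers already reported as SAEs have a follow-up rule, and deaths are tabulated separately. The 8.1.1 list of AE attributes also sends the investigator to 8.2.1 to judge seriousness, so some sites may classify such an event as serious despite the exemption. That softens the effect but adds to the inconsistency.

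Three stronger readings should be resisted:

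- That new cancers are exempt. They are not; the sentence covers progression only.
- That cancer deaths in benign-disease patients disappear from the report. SAP 7.4.2 shows them by indication.
- That the number of missed events can be estimated. Applying an assumed cancer incidence to the enrolled patients would model new cancers, which are mostly covered, rather than pre-existing ones. The documents give neither patients by indication nor the frequency of prior cancer.

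Nor do the documents present malignancy as a leading safety question for pasireotide: none of the AESI categories in SAP Attachment 8.2 is a neoplasm category.

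**Conclusion.** The point holds as a scope error and an internal conflict. Protocol 8.1.1 exempts documented progression of, and death from, any malignancy, while 8.2.1 and 8.2.2 require such events to be reported when they meet the SAE definition. The conflict matters because SAEs form part of the primary endpoint and because parent studies with only non-malignant indications are the majority (12 of 17).

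The consequence is misclassification and missing expedited reports, not disappearance from the data. It is firmest for non-study cancers that pre-date consent or whose diagnosis was not reported as an SAE. For cancers already reported as SAEs, sites have opposite instructions, and the result depends on which they follow. The conclusion assumes that sites apply 8.1.1 as written. The effect on the SAE counts cannot be sized from the documents and could be zero. Even so, a single suspected fatal case withheld from expedited reporting would matter.

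**What to change.** In Protocol 8.1.1, limit the sentence to progression, including fatal outcome, of the malignancy that is the patient's parent-study indication. State that progression of or death from any other malignancy is handled under 8.2.1 and 8.2.2, and cross-refer the three sections so that the follow-up rule in 8.2.2 is not contradicted.

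In the SAP, add a check before database lock: for patients with a benign indication, reconcile deaths, end-of-treatment reasons and neoplasm AEs against the SAE reports, and query any progression or cancer death without one. The SAP 7.4.2 death listing supplies part of this. The check is useful even if the protocol can no longer be amended.

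The cost is one protocol sentence with cross-references, one data check and possibly a few more SAE reports. No planned analysis changes.
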